9.1 Adverse Events (AE)

9.1.1 General

All adverse events and special reporting situations, whether serious or non-serious, are recorded on eCRF from the time a signed and dated ICF is obtained until completion of the participant's last study related procedure, which may include phone call contact for the follow-up of safety.

9.1.2 Definitions

Coding of an AE

The verbatim terms used in the eCRF by investigators to identify AEs will be coded (for system organ class (SOC-Med) and preferred term (PT)) using the Medical Dictionary for Regulatory Activities (MedDRA).

Phase allocation of an AE

AEs will be allocated to different study phases based on their start date/time. (Note: In addition to the date information, time information is also taken into account to allocate AEs to phases.)

In general, the following rule is used to allocate a phase to an AE:

Rule: phase start date/time \leq AE start date/time \leq phase end date/time

If the start date/time of an AE is before the start of the treatment phase, then it is allocated to the screening phase. If AE onset is on or after the treatment phase start date/time and prior to follow-up phase start date/time, then AE is allocated to treatment phase. If AE onset date/time is on or after the start of follow-up phase, then AE is allocated to follow-up phase. In case of incomplete AE dates and or times (i.e. time and/or day and/or month and/or year missing) the following conventions are used:

- In case of partial AE start dates and or times, the events are allocated to the phases using the available partial information on start and end datetime; no imputation will be done. If, for instance, for the AE start date only month and year are available, these data are compared to the month and year information of the phases. This rule may result in an AE to be allocated to more than one phase. In case of a completely missing AE start date, the event is allocated to the treatment phase, except if the end date of the AE falls before the start of the treatment phase.
- In case of a completely missing AE end date, the following rules apply:
 - in case the date is identified as unknown then date will remain as missing,

- in case the date is not flagged as unknown the date is assumed to be the cut-off date of the analysis for participants still ongoing in the study, and the end date of the last phase for participants who discontinued or completed the study.

Examples:

Screening phase: start date: 02JAN2017, end date: 28JAN2017

Treatment phase: start date: 29JAN2017, end date: 12AUG2017

- 1) Adverse event: start date: JAN2017, end date: 15JUL2017
As the AE start date only has information about month and year, only this information will be used from the phases and therefore the AE will be assigned to the screening phase as well as to the treatment phase.
- 2) Adverse event: start date: JAN2017, end date 27JAN2017 As the AE ends before or at the start of the treatment phase, it is only assigned to the Screening phase.

Attributes of an adverse event

For the analysis, the following attributes are assigned to an adverse event:

- Study Phase of an AE (Screening, Treatment and Follow-up phase),
- Verbatim Term, SOC-Med and PT,
- Serious AE (Yes/No), if yes AEs will be listed as well,
- AE grade (Grades 1, 2, 3, and 4),
- Relation to study treatment (related, not related),
- Outcome of AE (Fatal, Recovered/Resolved, not recovered/not resolved, recovering/resolving, unknown),
- AE leading to death (Yes/No),
- AE of special interest (Serious Infections, Hypersensitivity, Hematologic Events, Liver Enzymes).

9.1.3 Analysis Methods

There will be no formal statistical testing for the AEs.

A summary table will be generated for the following attributes of AEs for 2 study phases (treatment phase, follow-up phase):

- any AE,
- serious AEs,
- AEs leading to death,
- AEs with grade ≥ 3 ,
- AEs with grade ≥ 3 and related to study drug,
- AEs related to study drug,
- AEs of special interest,
- AEs of special interest and related to study drug.

AE incidence tables will be generated showing the SOC-Med and PT separately in two phases (treatment and follow-up), in descending order of frequency in Sirukumab treatment arm. For each AE, the percentage of participants who experience at least 1 occurrence of the given event will be summarized. The tables will be provided for the following attributes:

- AEs by SOC-Med and PT,
- Serious AEs by SOC-Med and PT,
- AEs of special interest,
- AEs related to study drug,
- AEs with Grade ≥ 3 ,
- AEs leading to death.

Separate listings of participants with serious AE, AEs leading to death and AE ≥ 3 grade and AE related to study drug will be generated.

A table showing number of participants with SOC-Med of Infection and Infestation vs Lymphocytopenia Grade 3-4 during treatment phase will be generated.

Subgroup Analysis:

Tables for the following AE attributes will be generated by 2 subgroups: (Age: < 65 , ≥ 65 years, CRS score at baseline: ≤ 3 , ≤ 4 , 4, 5).

- Serious AEs,
- AEs of special interest, AEs related to study drug,
- AEs with Grade ≥ 3 ,
- AEs leading to death.

9.2 Clinical Laboratory Tests

9.2.1 General

The laboratory parameters are measured pre- and post-dose multiple times during the study. Some of these parameters are considered biomarkers for this study and their analyses are described in Section 7 “Biomarkers” of this document. This section describes the analyses of laboratory parameters whose test samples are collected at local labs and are not described under biomarkers.

9.2.2 Data Handling Rules

For lab tests from local labs the local lab reference ranges will be used to determine the lab abnormalities.

Imputations of numerical values expressed as characters

In case a laboratory test result is censored (no numeric value is available, but only a verbatim term), the following rules are applied:

- ‘ $<x$ ’ or ‘ $>x$ ’: a numeric value will be imputed by the cut-off value decreased or increased with one unit respectively

- ‘ $\leq x$ ’ or ‘ $\geq x$ ’: imputation by x.

Toxicity grades and abnormalities for laboratory parameters

The laboratory toxicity will be determined according to the criteria specified in the adult toxicity grading table by ‘Division of Microbiology and Infectious Diseases’ (DMID). In case no toxicity grades are defined for a test, the abnormalities (above/below normal range) will be used.

In determining toxicity grades/abnormalities for each subject the following rules are applied:

- Baseline toxicity grade/abnormality will be based on the baseline value (see section 4.1 for the baseline definition).
- Worst grades/abnormalities during treatment phase are determined over the treatment phase, including all scheduled and unscheduled measurements of that phase.
- The abnormalities “abnormally low” and “abnormally high” are considered equally important, i.e. if a subject has an abnormally low as well as an abnormally high value post-baseline, both abnormalities will be shown in the tables. (This implies that the sum of the percentages can be more than 100%).
- If, for a specific test, the grading list provides distinct limits for abnormally low (=hypo) values as well as for abnormally high (=hyper) values, this test should be repeated for hyper and hypo limits separately in cross-tabulations.

Treatment-emergent definition for toxicity grades and abnormalities

A toxicity grade/abnormality will be considered treatment-emergent if it is worse than the baseline grade/abnormality. If the baseline grade/abnormality is missing, the abnormality is always considered as treatment-emergent. A shift from “abnormally low” at baseline to “abnormally high” post-baseline (or vice versa) is also treatment-emergent.

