Six SAEs were reported in Part A and 3 SAEs were reported in Part B. The single death in this study, due to a car accident, was considered to be not related to the administration of sirukumab. Two SAEs of infection were reported: pneumonia that was considered to be probably related to sirukumab administration and a bacterial infection of an iatrogenic wound that was considered to be unlikely related to sirukumab administration. Neutropenia and thrombocytopenia were reported more frequently in participants in the sirukumab groups than in the placebo groups in both lupus populations. Compared with the placebo group, participants with CLE in the 1 and 4 mg/kg sirukumab groups reported a relatively higher number of skin-related AEs that were considered to be reasonably related to sirukumab, whereas the 10 mg/kg group did not report any reasonably related skin events.

Participants who received sirukumab showed immediate stable and sustained decreases in WBC, ANC, and platelets at all individual dose levels, while participants in the placebo group showed no change in results. The decreases were not dose dependent. There was little to no clear temporal association between low neutrophil counts and the occurrence of infections. Two participants in the Part B SLE cohort were discontinued from administration because of low ANC and platelet counts, but no immediate apparent clinical symptoms were associated with these low values.

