Eight of 21 participants (38.1%) from the sirukumab group and no participant from the placebo group reported treatment-emergent serious infections. All serious infections occurred after patients had received at least 4 doses of sirukumab at Week 12. The most frequently reported treatment-emergent serious infections were pneumonia (3 of 21 participants [14.3%] reported pneumonia and 1 of 21 participants [4.8%] reported pneumonia haemophilus), and cellulitis (2 of 21 participants [9.5%]). In addition, 1 participant had a severe infusion reaction (anaphylactic reaction) following the first administration of sirukumab.

A higher reduction in absolute neutrophils count and WBC count from baseline was observed in the CNTO136 group as compared with the placebo group over time. No noteworthy changes from baseline were observed in other hematology parameters. For neutrophils, there was a 24.88% decrease from baseline at Day 4 and a 27.67% decrease at Week 4. Further decrease varied during the study until Week 40 with a decrease of 31.56%. For neutrophils (decreased), there were no toxicities observed in the placebo group whereas, all toxicities grades were observed in the CNTO136 group: Grade 1 (4 of 21 participants [20.0%]), Grade 2 (8 of 21 participants [40.0%]), Grade 3, and Grade 4 (each observed in 1 of 21 participants [5.0%]). For WBC (decreased), no Grade 4 toxicity was observed in either of the treatment groups. A similar percentage of participants had Grade 1 toxicity (5 of 21 participants [25.0%] in the CNTO 136 group and 1 of 4 participants [25.0%] in the placebo group). No Grade 2 or 3 toxicities were observed in the placebo group whereas, 10 of 21 participants (50.0%) had Grade 2, and 2 of 21 participants (10.0%) had Grade 3 toxicity in the CNTO 136 group. For lymphocytes (decreased), no Grade 4 toxicity was observed in the placebo group whereas, 1 of 21 participants (5.0%) had Grade 4 toxicity in the CNTO 136 group. A higher percentage of participants had Grade 2 and Grade 3 (each observed in 6 of 21 participants [30.0%]) toxicities in the CNTO 136 group whereas, in the placebo group 1 of 4 participants (25.0%) had Grade 2 toxicity and 2 of 4 participants (50.0%) had Grade 3 toxicity. There were few participants in the sirukumab group with elevated toxicity grades for liver function

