Absolute Lymphocyte Count, Low ^a aged >5 years (not HIV-infected)	600 to <650 / mm ³ 0.600×10^9 to $<0.650 \times 10^9$	500 to <600 / mm ³ 0.500×10^9 to $<0.600 \times 10^9$	350 to <500 / mm ³ 0.350×10^9 to $<0.500 \times 10^9$	<350 / mm ³ $<0.350 \times 10^9$
Platelets	75,000- 99,999/ mm ³	50,000- 74,999/ mm ³	20,000-49,999/ mm ³	<20,000/ mm ³
WBCs	11,000-13,000/ mm ³	13,000- 15,000 / mm ³	15,000- 30,000/ mm ³	>30,000 or <1,000 / mm ³
% Polymorphonuclear Leucocytes + Band Cells	> 80%	90 – 95%	>95%	-----
Abnormal Fibrinogen	Low: 100-200 mg/dL High: 400-600 mg/dL	Low: <100 mg/dL High: >600 mg/dL	Low: < 50 mg/dL -----	Fibrinogen associated with gross bleeding or with disseminated coagulation
Fibrin Split Product	20-40 mcg/ mL	41-50 mcg/ mL	51-60 mcg/ mL	> 60 mcg/ mL
Prothrombin Time (PT)	1.01 - 1.25 x ULN	1.26-1.5 x ULN	1.51 -3.0 x ULN	>3 x ULN
Activated Partial Thromboplastin (APPT)	1.01 -1.66 x ULN	1.67 - 2.33 x ULN	2.34 - 3 x ULN	> 3 x ULN
Methemoglobin	5.0 - 9.9 %	10.0 - 14.9 %	15.0 - 19.9%	> 20.0 %

^a Added by the sponsor, based on Division of AIDS (DAIDS) table for grading the severity of adult and pediatric adverse events, version 2.1, July 2017.²¹

CHEMISTRIES				
	Grade 1	Grade 2	Grade 3	Grade 4
Hyponatremia	130-135 mEq/ L	123-129 mEq/ L	116-122 mEq/ L	< 116 mEq/ L or abnormal sodium with mental status changes or seizures
Hypernatremia	146-150 mEq/ L	151-157 mEq/ L	158-165 mEq/ L	> 165 mEq/ L or abnormal sodium with mental status changes or seizures
Hypokalemia	3.0 - 3.4 mEq/ L	2.5 - 2.9 mEq/ L	2.0 - 2.4 mEq/ L or intensive replacement therapy or hospitalization required	< 2.0 mEq/ L or abnormal potassium with paresis, ileus or life-threatening arrhythmia
Hyperkalemia	5.6 - 6.0 mEq/ L	6.1 - 6.5 mEq/ L	6.6 - 7.0 mEq/ L	> 7.0 mEq/ L or abnormal potassium with life-threatening arrhythmia
Hypoglycemia	55-64 mg/dL	40-54 mg/dL	30-39 mg/dL	<30 mg/dL or abnormal glucose with mental status changes or coma
Hyperglycemia (nonfasting and no prior diabetes)	116 - 160 mg/dL	161- 250 mg/dL	251 - 500 mg/dL	> 500 mg/dL or abnormal glucose with ketoacidosis or seizures
Hypocalcemia (corrected for albumin)	8.4 - 7.8 mg/dL	7.7 - 7.0 mg/dL	6.9 - 6.1 mg/dL	< 6.1 mg/dL or abnormal calcium with life-threatening arrhythmia or tetany

CHEMISTRIES (continued)				
	Grade 1	Grade 2	Grade 3	Grade 4

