9.2.3 Analysis Methods

Tables showing n and percent of participants with treatment-emergent worst toxicity grades (for tests with defined toxicity grades) and treatment-emergent worst abnormalities (for tests without a defined toxicity grades) during treatment phase will be generated.

A shift table showing the number and percent of participants with different toxicities at baseline vs treatment phase will be presented for lab tests with defined toxicity grades.

Shift tables showing n and percent of participants with various levels of abnormalities for Troponin-I and -T during treatment phase versus baseline will be generated.

Two eDISH plots showing peak total bilirubin vs peak ALT (and separately for peak AST) measurements during the treatment phase will be generated. Peak values (using \log_{10} scale) on the plot will show the maximum values that occur post-baseline during treatment phase (not necessarily concurrent events). Points on the plot will be distinguished for the two treatment groups. Two reference lines at 2xULN for total bilirubin and at 3xULN for ALT/AST will be shown on the plots. These reference lines will divide the plot into 4 sections showing (1) Hyperbilirubinemia, (2) Hy's Law range, (3) Normal range, and (4) Temple's Corollary range.

A listing of participants with treatment-emergent toxicities/abnormalities will be provided. This listing will include all other timepoints for the corresponding participant/lab test.

A listing of participants with Grade 3 or higher toxicity laboratory values will be provided.

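### Total WBC between 1,000/mm³ and the lower limit of normal gets no grade in the SAP laboratory outputs, so a fall below normal is not counted

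*SAP*

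**What the plan says.** **Grading rule.** SAP 9.2.2 states: "The laboratory toxicity will be determined according to the criteria specified in the adult toxicity grading table by" DMID. It adds one fallback: "In case no toxicity grades are defined for a test, the abnormalities (above/below normal range) will be used". A further rule covers tests where "the grading list provides distinct limits for abnormally low (=hypo) values" as well as limits for high values. Such tests are repeated for the low and the high side in cross-tabulations.

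**Outputs.** SAP 9.2.3 gives worst-grade tables and a grade shift table to tests that have grades. It gives worst-abnormality tables to tests that do not, plus separate shift tables for troponin. It plans two listings: treatment-emergent findings, and values of grade 3 or higher. SAP 4.2 also summarizes baseline WBC by DMID grade.

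**The WBC row.** In Protocol Appendix 8 (Section 10.8), WBC grades 1, 2 and 3 are 11,000-13,000, 13,000-15,000 and 15,000-30,000/mm³. Grade 4 is ">30,000 or <1,000". The lymphocyte row of the same table, which grades low values, carries the footnote "Added by the sponsor, based on Division of AIDS (DAIDS) table for grading the severity of adult and pediatric adverse events". No low-side row was added for WBC.

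**Earlier experience.** Protocol 2.1.1 reports for C0136T03: "Participants who received sirukumab showed immediate stable and sustained decreases in WBC, ANC, and platelets at all individual dose levels", with no change on placebo. For CNTO136LUN2001 it reports graded WBC decreases on sirukumab and notes: "For WBC (decreased), no Grade 4 toxicity was observed in either of the treatment groups".

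**The concern.** The fallback to normal ranges asks whether a test has any grades, not whether the relevant side of the test is graded. WBC passes that question on the strength of its high-side grades, and so loses its below-normal classification. Almost the whole low side is then unclassified, for a drug whose protocol describes WBC decreases.

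At stake is the reading of the WBC rows in the safety tables. They would show high counts by arm, and of low counts only those under 1,000/mm³. A participant graded high at baseline could fall below normal and appear in the shift table as improved.

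**Working it through.** No sample size, power or alpha is involved. The check applies the printed limits and the SAP rules to example values.

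**1. Inputs**
- WBC, neutrophil (ANC) and lymphocyte limits: Protocol Appendix 8.
- Grading, fallback, worst-value and treatment-emergent rules: SAP 9.2.2.
- Outputs: SAP 9.2.3.
- LLN for WBC: not in the documents, because local ranges apply. Assumed to be 3,500 to 4,500/mm³ for illustration.

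**2. WBC limits applied**

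| WBC (/mm³) | DMID grade |
|---|---|
| 900 | 4 |
| 1,000; 1,500; 2,000; 3,000 | none |
| 12,000 | 1 |
| 14,000 | 2 |
| 20,000 | 3 |
| 31,000 | 4 |

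The low values left unclassified run from 1,000 to 3,500, 4,000 or 4,500/mm³ for an assumed LLN of 3,500, 4,000 or 4,500.

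**3. Do other SAP rules close the gap?**
- *Fallback:* it applies only to a test with no grades. WBC has grades.
- *Low/high split:* it separates limits that exist and creates none. A low-WBC table would contain only values below 1,000.
- *Treatment-emergent rule:* the finding must be worse than the baseline grade. An ungraded value cannot be.
- *Listings:* an ungraded value triggers neither. It would show only if the participant were listed for another WBC result, since the treatment-emergent listing prints all time points for that test.

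**4. Shift table**

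The worst grade is taken over all treatment-phase values. Take baseline 14,000 (grade 2) and every post-dose value at or above 1,000 and below 11,000, for example a fall to 2,000. The worst post-dose result is no grade, so the shift is from grade 2 to none. If any post-dose value is 11,000 or more, or under 1,000, this does not happen.

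**5. How far do the component rows cover it?**

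ANC is ungraded above 1,500, and lymphocytes are ungraded from 650. Neutrophils plus lymphocytes cannot exceed total WBC. If both components are ungraded, WBC must exceed 1,500 + 650 = 2,150. With a differential on the same sample, a WBC of 2,150 or less therefore always carries a low-side grade in at least one component. Above 2,150 it may carry none:

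| WBC | ANC | Lymphocytes | Grades (WBC / ANC / lymphocytes) |
|---|---|---|---|
| 2,000 | 1,200 | 600 | none / 1 / 1 |
| 2,500 | 1,550 | 700 | none / none / none |

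**6. Context from CNTO136LUN2001**

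Graded WBC decreases on sirukumab: 5 + 10 + 2 = 17 participants (grades 1, 2, 3). That is 17/21 = 81%, or 17/20 = 85% on the denominator the printed percentages imply (5 participants shown as 25.0%). On placebo, 1 of 4 had grade 1 and none had grade 2 or 3, so the grade 2-3 comparison is 12 against 0. The grading scale is not given.

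**The case against.** The strongest reply is that the clinically important parts of the effect stay visible. The hematologic risks named in Protocol 8.3.6 and Appendix 7 are neutropenia and thrombocytopenia, not leukopenia. ANC, lymphocytes and platelets are all graded on the low side, grade 3-4 neutropenia and lymphocytopenia is a secondary safety endpoint, and hematologic events are of special interest in the adverse event tables. This stands, and it confines the point to total WBC.

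Second, the protocol promises more than the SAP repeats: descriptive laboratory statistics (Synopsis) and a listing of results outside the reference ranges (9.4.6). SAP Section 1 says it is to be read together with the protocol. This stands in part. The commitments are not withdrawn, but SAP 9.2.3 plans neither output, and a listing gives no count by arm.

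Third, SAP 9.2.2 says that local reference ranges determine abnormalities, and Protocol 9.4.6 sends results to normal ranges when no grading is available, which could be read value by value. This does not rescue the plan. The SAP fallback is worded per test, and both documents reserve abnormality tables for tests without grades.

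Three stronger inferences are tempting, and the documents do not support them:
- *The Data Monitoring Committee would see a false benefit.* This SAP covers the primary and final analyses. The committee works under its own charter, and nothing shows that its outputs use these tables.
- *This trial would count none of the 17 CNTO136LUN2001 cases.* That assumes grade 4 there also meant below 1,000/mm³. The study gave 10 mg/kg every 4 weeks to lupus nephritis patients on background immunosuppressants, against a single 5 mg/kg dose here. Five of the 17 are grade 1 cases, which the protocol describes as similar in frequency to placebo.
- *Leukopenia cannot appear at all.* A WBC below 1,000/mm³ is grade 4.

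**Conclusion.** The gap is real but narrow. In the SAP laboratory tables, shift table and listings, a total WBC from 1,000/mm³ to the LLN has no grade and cannot be treatment-emergent. A participant graded high at baseline whose post-dose values all lie from 1,000 to below 11,000 is shown as improved, even if WBC falls below normal.

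The unclassified band is 1,000 to about 3,500-4,500/mm³, on an assumed LLN. At or below 2,150/mm³ at least one of ANC and lymphocytes must be graded, given a differential on the same sample. Above that, a below-normal WBC can go ungraded in all three rows.

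The evidence that the low side matters comes from repeat-dose lupus studies. The protocol's summary of the single-dose IV study in healthy participants describes neutrophil and lymphocyte findings but no WBC fall. The CNTO136LUN2001 counts are context, not a forecast. A reader might infer that the drug's hematologic effect as a whole is concealed. It is not, because its neutrophil, lymphocyte and platelet parts are graded. The point is still worth correcting, because a stated rule misclassifies low WBC and the remedy is cheap.

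**What to change.** In SAP 9.2.2 and 9.2.3:
- State that WBC is reported separately for low and high values. Tabulate treatment-emergent WBC below the local LLN by arm, beside the DMID high-side grades. Keep values below 1,000/mm³ as grade 4 on the low side.
- Apply the same split to the WBC shift table, so that a move from high to low is not shown as improvement.
- Carry over from the protocol the listing of results outside reference ranges and the descriptive statistics for laboratory parameters.

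A graded low-WBC row borrowed from the DAIDS table is not proposed, because the documents show only that its lymphocyte limits were used.

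Cost: a sentence in each section, one or two more tables, and the outputs the protocol already promises. WBC and local ranges are already collected. Sample size, power and alpha are unaffected.
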